As noted in Figure 1, the study includes three of the possible four Ifaa intervention combinations. Characterizing the impact of livelihoods programming without the Ifaa enhanced intervention was not considered a priority.

Figure 2. Study Flow Diagram

A longitudinal cohort design will be used to compare the effectiveness of three Ifaa intervention packages among PSNP beneficiaries: 1) the Ifaa basic package; 2) enhanced package without livelihoods; and 3) enhanced package with livelihoods. Under this approach, the enrolled households will have either a pregnant woman or children <36 months of age. Households will be followed over a two-year period, with the baseline and endline survey conducted at a similar time

³ Community led complementary feeding sessions (CCFLS) is a six month program targeted at children at risk of acute malnutrition or recently discharged from a malnutrition treatment program. It includes caregiver training on child feeding practices and growth monitoring and is a six month intervention, with intensive services/training in the first month and follow up monitoring.

period in the calendar year to avoid seasonal changes in food security. The magnitude of change in key indicators over time will be assessed for each group; if needed, adjusted models will be used to account for baseline differences between groups. Outcome measures of focus are aligned with Ifaa indicators and include measures of household food consumption and child diet. To ensure adequate geographic coverage, a **stratified sampling design** will be used as follows:

- (1) **Kebele Selection.** Two kebeles per intervention arm will be purposively selected in each of the nine woredas with the aims of 1) of maximizing geographic similarity in terms of agro-ecological zone (lowland, midland, highland) and remoteness; and 2) ensuring sufficiently large beneficiary population is available for sampling purposes. In the case of smaller kebeles where it appears unfeasible to attain three clusters, the sample may be distributed across additional kebeles within the woreda.⁴

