The primary outcome measure for the evaluation is improvement in household food security. To align the evaluation with project aims, key project indicators are used as study outcome measures. These include: 1) At the household level, **Poor or Borderline Food Consumption Score (FCS)**; and 2) at the individual level, change in **minimum dietary diversity among children <5 years**. Sample size calculations are presented in **Table 3** (following page) and are based on both primary and secondary outcome measures for within-group change over time using available data from the Ifaa baseline along with Ifaa targets for change. Assumptions included the following: 1) power ($1-\beta$) of 80% and significance of $\alpha=0.05$; 2) a design effect of 1.5 to take into account differences across Kebeles; and 3) expected absolute change in proportion of primary/secondary outcome; and 4) loss to follow up rate of 20% over the study period. Based on initial sample size projections, a minimum sample size of 915-1,070 households per group and 2,745-3,210 is required which is sufficient to detect differences $\geq 8\%$ between groups for both the primary and secondary outcome measures.

We are proposing a planned sample size of 1,080 per group or 3,240 households total. Given challenges in field coordination across multiple teams and delays in data quality monitoring reviews, it is possible that several additional households could be enrolled in a kebele. To ensure that the approved sample size is not inadvertently exceeded due to communication challenges we are requesting approval for a **maximum sample of 3,500 households**.

Table 3: Sample Size Calculations

| | Baseline Value | Magnitude of Change | Sample Size per Group | Total Sample Size |
|--|----------------------------|---------------------|-----------------------|-------------------|
| | 34% in Oromiya (WFP, 2021) | -8% | 915 | 2745 |

⁴ The number of beneficiary households per kebele ranges from approximately 75 to 650; given inclusion criteria it is unlikely that smaller kebeles will have 60 eligible households, in which case cluster(s) will be assigned in additional kebeles in the woreda.

⁵ In the baseline survey, the average number of children <5years in PSNP households was 0.83 and 14% of the population was <5 years of age. Based on this we estimate that 15-25% of Ifaa beneficiary households will meet study inclusion criteria.

| | | | | | |
|---|---|-------|------|------|--|

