| Poor or borderline household food consumption (FCS) | 48% in E Hararghe (UMN , 2020) | -10% | 609 | 1827 | |
| | | -12% | 402 | 1206 | |
| Minimum dietary diversity among children <5 years | | -8% | 1070 | 3210 | |
| | | -10%* | 674 | 2022 | |
| | | -12% | 481 | 1443 | |
| 19.5% in Oromya (2019 DHS) | +8% | 785 | 2355 | | |
| | +10% | 533 | 1599 | | |
| | +12% | 366 | 1098 | | |

*denotes Ifaa change target

C. Does your study meet the NIH definition of “clinical trial”: “A research study in which one or more human subjects are prospectively assigned to one or more interventions (which may include placebo or other control) to evaluate the effects of those interventions on health-related biomedical or behavioral outcomes”?

Per the JHSPH IRB’s determination, this study meets the definition of a clinical trial.

IV. Participants:

A. Inclusion Criteria:

- Households are PSNP clients
- Households are Ifaa Project beneficiaries that are planned participants in: 1) SILC groups (Ifaa Basic); 2) SILC Groups AND Care Groups (Ifaa and Enhanced); or 3) SILC groups AND Care Groups AND a Livelihoods Pathway.
- Households have a pregnant woman OR at least one child <36 months of age
- Households have an adult member that is capable of giving informed consent and completing an interview

B. Exclusion Criteria:

- Child headed households (all members age 17yrs or less)
- Individuals not mentally able to give informed consent and complete an interview

V. Study Procedures:

A. Recruitment Process:

1. *Describe how you will identify, approach, and inform potential participants about your study. Include details about who will perform these activities and their qualifications.*

The JHU team will receive the list of PSNP households/Ifaa beneficiary households living in the sampled Ifaa Kebeles from CRS Ethiopia team. Trained enumerators will conduct a verification exercise and visit households on the list to confirm eligibility. After the verification exercise, a second visit will be made to selected households where enumerators will explain the study purpose, households will have the opportunity to ask questions, and oral consent will be obtained. Any adult household member will be eligible to participate, however, preference will be given to caretakers of young children/pregnant women followed by household heads.

2. *Address any privacy issues associated with recruitment.*

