The study households will be visited at two time points prior to intervention start up and again after 24 months of intervention exposure to ensure data is collected during the same season. The location of each household will be recorded with GPS and a hand-drawing map to ensure feasibility of follow up. A structured questionnaire will be used to collect data at both the household and individual child level, with data collected for all children <5 years of age in the household. The baseline and endline questionnaire will include the same content, with the exception of a module that will be added (in a future modification) to characterize Ifaa intervention participation and satisfaction. Questionnaire content will include background information on primary care taker (e.g. literacy, age, pregnancy status) and household characteristics (e.g. size, residence location) and household food security measures including [Food Consumption Score](#), [Household Hunger Scale](#), and [Coping Strategies Index](#). For children, individual level information to be collected includes child background information (e.g. age, sex); [Infant and Young Child Feeding Indicators](#); and anthropometric measurements (weight, height/length, arm circumference).

2. *Describe the number and type of study visits and/or contacts between the study team and the participant, how long they will last, and where/how they will take place.*

Each study participant will have three contacts by enumerators, two at baseline including one to determine eligibility and one to complete the interview (May 2023) and one at final evaluation (May 2025). All study visits will be made at the participant's residence. The survey will take 40 to 50 minutes and each interaction is anticipated to be one hour or less.

2. *Describe the expected duration of the study from the perspective of the individual participant and duration overall.*

From the participant's perspective, the overall study duration will be two years. The baseline survey and consent process will take less than one hour and the same process will be repeated at the endline survey.

3. *Provide a brief data analysis plan and a description of variables to be derived.*

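### Within-arm change in child dietary diversity mixes ageing of the under-five sample with any programme effect, because the adjustment rule cannot pick up an age shift between rounds

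*Combined protocol and SAP*

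**What the plan says.** - **Who enters.** IV.A Inclusion Criteria: "Households have a pregnant woman OR at least one child <36 months of age".
- **Who is measured.** V.C Study Implementation plans a baseline survey and a second one after 24 months of exposure, "with data collected for all children <5 years of age in the household". Child age and sex are among the items collected.
- **What is reported.** III.A Study Design Overview: "The magnitude of change in key indicators over time will be assessed for each group".
- **What is sized.** III.B Sample Size bases the calculations on "within-group change over time using available data from the Ifaa baseline along with Ifaa targets for change". One of the two outcomes is "minimum dietary diversity among children <5 years". Its Table 3 rows start at 19.5% and ask for 785, 533 and 366 per group for rises of 8, 10 and 12 points.
- **What is adjusted for.** The data analysis plan in V.C says that background variables may be controlled for or used to disaggregate. It commits only to adjusting for those that differ significantly between groups at baseline.
- **What the effect model estimates.** The same section takes the programme effect from a group-by-time interaction, that is, change in an intervention group set against change in the comparison group.

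**The concern.** The cohort is one of households, but the child outcomes are read off whichever children are under five at each visit. That group does not keep the same age mix. Enrolment selects households for having very young children, and two years later those children are two years older.

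If dietary diversity varies with age, its prevalence will move between rounds with no programme at all. The adjustment rule compares arms with each other at one time point. Child age can be perfectly balanced across arms at baseline, and so fail the rule's test, while changing from baseline to endline in all three arms.

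At stake is the reading of the within-arm changes. They are a planned output and the quantity behind Table 3, and they will naturally be compared with the project's change targets.

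**Working it through.** **1. Reproduce the plan's figure.** Inputs from III.B: 19.5% to 27.5%, 80% power, alpha 0.05 (two-sided assumed), "a design effect of 1.5 to take into account differences across Kebeles", and 20% loss. The pooled two-proportion formula is

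n = [1.96 × √(2 × p̄ × (1−p̄)) + 0.842 × √(p1(1−p1) + p2(1−p2))]² / (p2−p1)²

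With p̄ = 0.235:

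n = [1.96 × √0.3596 + 0.842 × √0.3564]² / 0.0064 ≈ 440

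440 × 1.5 × 1.2 = 792, against 785 in Table 3. The powered quantity is therefore a plain baseline-versus-endline difference in one group, with no allowance for age.

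**2. Age shift among index children.** Ages 0-35 months become 24-59 months. If ages are uniform (assumption), 24/36 = 67% are under 24 months at baseline and none are at endline. Siblings and births pull this back: siblings of 36-59 months count at baseline and then leave, while children born after enrolment count only at endline.

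**3. Change from ageing alone.** The documents give no age-specific prevalence, so two patterns are assumed:
- *Flat:* 0% under 6 months, 23.4% at every older age (set so that index children average 19.5% at baseline).
- *Steep:* 0% under 6 months, 10% at 6-11, 20% at 12-23, 26% at 24-35, 28% from 36 months.

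Means by age group, with uniform ages:

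| Pattern | Index at baseline, 0-35 m | Siblings at baseline, 36-59 m | Index at endline, 24-59 m | Births at endline, 0-23 m |
|---|---|---|---|---|
| Flat | 19.5% | 23.4% | 23.4% | 17.55% |
| Steep | 17.0% | 28.0% | 27.3% | 12.5% |

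Let s be older siblings and b new births per index child (both assumed). Then baseline = (index + s × sibling)/(1+s), endline = (index + b × birth)/(1+b), and the ageing-only change is the difference.

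| s | b | Flat | Steep |
|---|---|---|---|
| 0.2 | 0.2 | +2.3 | +6.0 |
| 0.3 | 0.3 | +1.7 | +4.4 |
| 0.3 | 0.5 | +1.1 | +2.9 |
| 0.5 | 0.5 | +0.7 | +1.7 |

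For example, steep with s = b = 0.2: baseline (17.0 + 5.6)/1.2 = 18.8; endline (27.3 + 2.5)/1.2 = 24.9; change +6.0 points.

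**4. What that does to a within-group test.** The effective number per group is 1,080 × 0.8 / 1.5 = 576, taking one child per household and treating the rounds as independent samples. Starting from 19.5% with no programme effect, the chance of a significant rise is about 6% for an ageing change of 1 point, 13% for 2, 38% for 4 and 68% for 6. The nominal chance of a false rise is 2.5%.

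**5. The group-by-time contrast.** If every arm has the same ageing change a, the contrast is (programme change + a) − (comparison change + a), and a drops out on the risk-difference scale. On a logit scale, equal shifts in risk from different starting prevalences are unequal shifts in log odds, so cancellation is not exact. The GEE link is not stated.

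**The case against.** The strongest reply is that the plan does not take its programme effect from within-arm change. A reader might infer that a rise due to ageing would be reported as programme effect. For the planned model the documents do not support that: the effect is the group-by-time interaction, and ageing common to all arms largely cancels there. The arms share one eligibility rule, one survey calendar and one 24-month interval, and kebeles are chosen for geographic similarity. Purposive choice does not guarantee equal age shifts, but the documents give no reason to expect unequal ones. This part of the reply stands.

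A reader might also infer that ageing could exceed the 8-point change in Table 3. Index children alone would give +3.9 points (flat: 23.4 − 19.5) or +10.3 (steep: 27.3 − 17.0). Those figures leave out siblings and births, although the plan measures all under-fives; with them, no case worked above reaches 8 points.

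A third tempting step is to count growth in the sample-size target. Table 3 covers only food consumption and dietary diversity. Stunting and wasting are outcomes scored against WHO growth standards, and the documents give no figures on how their prevalence varies with age.

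Finally, age is collected and the plan permits its use, so it would be wrong to say that adjustment is ruled out. Permission is not commitment, however, and the only committed rule looks at the wrong contrast for change over time. That part of the concern survives.

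**Conclusion.** The concern holds for within-arm change in child dietary diversity and for the Table 3 rows built on it. As planned, that change cannot be read as progress, because it combines ageing of the sample with any programme effect.

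The size cannot be found from the documents. Under the assumed patterns it is roughly 1 to 6 points, or about one-eighth to three-quarters of the 8-point change. This rests on uniform ages, 0.2 to 0.5 siblings and births per index child, and infants under 6 months being counted as not achieving diversity. The last assumption matters. If those infants were outside the denominator, the flat pattern would give no ageing change, and the steep one would give +1.2 points at s = b = 0.5 [(27.3 + 6.25)/1.375 − (17.0 + 14.0)/1.333] and +4.1 at s = b = 0.2 [(27.3 + 2.5)/1.15 − (17.0 + 5.6)/1.033].

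The between-arm comparison is largely sound. Its remaining exposure is an unstated link function and any difference between arms in how the age mix shifts. The overall sample size is not driven by this outcome: the largest Table 3 requirement, 1,070 per group, is a food-consumption row.

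**What to change.** In the data analysis plan:

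1. In all child-outcome models, include child age in months at each survey (spline or fixed bands) and sex, whatever the baseline tests show.
2. Define the same fixed age band for each child indicator at both rounds, and say how infants under 6 months are treated.
3. Report within-arm dietary-diversity change standardised to the baseline age distribution.
4. State that the group-by-time contrast, not within-arm change, is the evidence of programme effect, and name the GEE link.

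The cost is wording and a little analysis time. Child age and sex are already collected, so no visit, question or sample-size change is needed.

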The outcome variables of focus at the household level will be measures of food security, including 1) [Food Consumption Score](#), 2) [Household Hunger Scale](#), and 3) [Coping Strategies Index](#). At the individual level, outcome variables of focus will include 1) [Infant and Young Child Feeding Indicators](#) (in particular achievement of minimum dietary diversity); and 2) prevalence of stunting and wasting, in accordance with the [World Health Organization Child Growth Standards](#). Background information on individual (e.g. literacy, age, pregnancy status) and household characteristics (e.g. size, residence location) will also be collected so that these can be controlled for or used for disaggregation in data analysis. All outcomes will be analyzed as continuous variables and as categorical variables based on pre-determined thresholds.

A descriptive analysis of household sociodemographic characteristics and outcome measures will be performed. Continuous variables will be presented as mean (SD) and categorical variables as n (%). ANOVA tests will be conducted for baseline characteristics and primary and secondary outcomes to examine the comparability between the three and intervention groups; individual/household characteristics with significant differences between groups at baseline will be controlled for in models that estimate the effect of the interventions.

The program effect on expected primary outcome measures will be estimated using mixed-effect linear regression analysis for continuous outcomes and Generalized Estimation Equation (GEE) model for binary outcomes. In the mixed-effects models, the random effect component included indicators to control for clustering at school levels. The fixed component included the intervention group (intervention vs. control), time and an interaction term for group and time. The GEE models will be used to examine binary outcomes with longitudinal data from both enrollment and endline. These models will estimate the change in a binary outcome among members of a given intervention group from enrollment to endline, compared to the change in the same outcome in the control. The GEE models also included an interaction term between the intervention group and time (baseline/endline).

5. **Answer the following if they are relevant to your study design:**

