A. *Describe any potential direct benefits the study offers to participants (“payment” for participation is not a direct personal benefit).*

All study participants benefit from the Ifaa project, however, there are no direct benefits to participating in this evaluation.

B. *Describe potential societal benefits likely to derive from the research, including value of knowledge learned.*

Findings from this study will contribute to an understanding of multi-sectoral development programming in Ethiopia. Knowledge learned will be applied by CRS in future programming and USAID in future funding calls for similar resilience programs.

IX. Payment or Token of Appreciation:

A. *Do you plan to provide a non-monetary token of appreciation (food, soap, tea, chlorine tablets, etc.) to study participants? If no payment is provided, the JHSPH IRB strongly encourages providing such tokens. If yes, please describe below.*

We do not plan to provide non-monetary tokens of appreciation due to the fact that households are receiving Ifaa benefits.

B. *If you plan to provide a monetary payment, describe the form, amount, and schedule of payment to participants. Reimbursement for travel or other expenses is not “payment,” and if the study will reimburse, explain.*

We do not plan to provide monetary payment due to the fact that households are receiving Ifaa benefits.

C. *Include the possible total remuneration and any consequences for not completing all phases of the research.*

Not applicable

X. Study Management:

A. **Oversight Plan:**

1. *Describe how the study will be implemented. List all parties, including collaborators and subcontractors, who will be “engaged” in the human subjects research project and their roles .*

The research will be led by a team from Johns Hopkins University (JHU) Department of International Health including [name], [name], and [name]. [name] will serve as the PI, [name] will lead on data quality monitoring and analysis, and [name], who is based in Ethiopia, will be responsible for training, data collection oversight and serve as the primary liaison between CRS and the data collection firm. The data collection firm will be jointly selected by CRS and JHU from a CRS list of pre-approved companies that have performed similar work for CRS previously. The data collection firm will be responsible for hiring enumerators which will have direct contact with study participants.

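### The sample size is worked out for change within one group, but the plan claims 80% power for 8-point differences between groups; for the planned group-by-time contrast on FCS, power is about 49–83%

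*Combined protocol and SAP*

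**What the plan says.** Section III.B (Sample Size) states that the calculations "are based on both primary and secondary outcome measures for within-group change over time using available data from the Ifaa baseline". The stated assumptions are 80% power, significance 0.05, a design effect of 1.5 and a "loss to follow up rate of 20% over the study period". Each row of Table 3 has one baseline proportion and one change. For an 8-point fall in poor or borderline FCS it gives 915 per group from 34% and 1,070 from 48%.

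The same paragraph then says that this number suffices for differences of 8% or more "between groups for both the primary and secondary outcome measures". The planned enrolment is 1,080 per group.

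The data analysis plan in section V.C sets a different contrast. For binary outcomes, the GEE models estimate change among "members of a given intervention group from enrollment to endline, compared to the change in the same outcome in the control". Both the GEE and the mixed models contain a group-by-time interaction. Section III.A adds that "if needed, adjusted models will be used to account for baseline differences between groups", but it does not name a baseline-adjusted endline comparison as the effect estimate.

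**The concern.** A before–after change in one group involves two proportions. A difference in change between two groups involves four. The number that gives 80% power for the first does not in general give it for the second, and the plan moves from one to the other without a calculation.

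The evaluation exists to compare packages. If a comparison comes out null, readers will set it against a stated 80% power that was never computed for it.

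The comparison arm is also treated: section VIII.A says "All study participants benefit from the Ifaa project". The only change in Table 3 marked with the note "denotes Ifaa change target" is a 10-point fall, in a table of within-group changes. An Enhanced arm that meets that target differs from Basic by 8 points only if Basic improves by no more than 2.

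**Working it through.** **Inputs from the plan.** Power 80%; alpha 0.05 (two-sided fits Table 3); design effect 1.5; loss 20%; 1,080 enrolled per group; FCS baselines 34% and 48%; difference 8 points. Table 3 is broken in the text available, so its rows were matched to baselines by fit.

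**Input not in the plan.** The baseline–endline correlation r within households. It is assumed here and shown at 0, 0.3 and 0.5.

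**Step 1: reproduce Table 3.** With n = (1.96 + 0.8416)² × (p1q1 + p2q2) / d², multiplied by 1.5 for design and 1.2 for loss:

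- 34% to 26%: n = 511; × 1.8 = 920 (plan: 915)
- 48% to 40%: n = 600; × 1.8 = 1,081 (plan: 1,070)
- 19.5% to 27.5%: n = 437; × 1.8 = 787 (plan: 785)

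So Table 3 is a two-proportion calculation with no credit for correlation. The loss factor is not fully recoverable. Over the nine rows, the ratio of the plan's figure to this formula runs from 1.77 to 1.91, against 1.80 for 1.5 × 1.2 and 1.875 for 1.5 / 0.8. With division by 0.8, the 48% to 40% row would need 600 × 1.875, about 1,126.

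**Step 2: variance of the planned contrast.** Let the comparison arm stay at p1 and the other arm move from p1 to p2 = p1 − 0.08. Then

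V = 2·p1q1·(1 − r) + p1q1 + p2q2 − 2r·√(p1q1·p2q2)

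| Baseline | r = 0 | r = 0.3 | r = 0.5 | Two-proportion variance |
|---|---|---|---|---|
| 48% | 0.989 | 0.692 | 0.494 | 0.490 |
| 34% | 0.866 | 0.606 | 0.433 | 0.417 |

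At r = 0 the ratio to the two-proportion variance is 2.02 (48%) and 2.08 (34%).

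**Step 3: power at the planned size.** Effective n per group = 1,080 × 0.8 / 1.5 = 576. Power = Φ(0.08 / √(V/576) − 1.96). For example, at 48% and r = 0: 0.08 / 0.0414 − 1.96 = −0.03, so power is 49%.

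| Baseline | Quantity | r = 0 | r = 0.3 | r = 0.5 |
|---|---|---|---|---|
| 48% | Power for 8 points | 49% | 64% | 78% |
| 48% | Detectable at 80% power | 11.6 | 9.7 | 8.2 |
| 34% | Power for 8 points | 54% | 69% | 83% |
| 34% | Detectable at 80% power | 10.8 | 9.1 | 7.7 |

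Detectable differences are in percentage points, with p2 re-evaluated at the detectable value. Power of 80% for 8 points needs r of about 0.53 (48% baseline) or 0.46 (34%).

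**Step 4: sensitivity.**

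- Design effect 1.0 for change (assumed, most favourable; effective n = 864): 66 / 81 / 92% at 48% and 71 / 86 / 95% at 34%.
- Enhanced falls 10 points from 48% and Basic falls 4 (assumed), a 6-point difference: 31 / 41 / 54%.
- Endline-only comparison of two groups at 1,080: 78% for 48% vs 40%, and 84% for 34% vs 26%.

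**Separate inconsistency, not used in these powers.** Section III.A says "Two kebeles per intervention arm will be purposively selected in each of the nine woredas". Table 2 lists eligible kebeles in eight woredas, and the kebeles named there already add up to the stated 34 Enhanced. At 60 households per kebele, 9 × 2 × 60 = 1,080 but 8 × 2 × 60 = 960 per arm. That lies within 915–1,070 but below both the planned 1,080 and the 1,070 of the 48% row.

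**The case against.** The strongest reply is that the two-proportion formula also describes a comparison of two groups at endline, where 1,080 gives 78% and 84%. On that reading the between-group sentence is about right, and within-group change, which Table 3 does size, is itself a stated aim in section III.A. This stands as far as it goes, but an endline-only comparison is not the analysis in section V.C.

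A second reply is that a shortfall is not proven. The same households are measured twice in the same season, so r = 0 is pessimistic. Stable differences between kebeles cancel in a change, so a design effect of 1.5 may be too high for this contrast. Both points are fair: with a design effect of 1.0 and r of 0.3 or more, power exceeds 80% at both baselines. But the plan states 1.5, claims no reduction and gives no r, so adequate power cannot be shown from it.

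Third, dietary diversity does better. Treated as one paired child per household, 19.5% to 27.5% gives 65 / 80 / 91% for r = 0 / 0.3 / 0.5. The plan does not give the number of paired children per household, so this is only indicative, and it does not rescue the claim for FCS.

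Finally, the scenario in which Basic improves by 4 points is an assumption. It illustrates the problem; the conclusion does not depend on it.

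**Conclusion.** The concern holds. The plan gives a power for one contrast and plans to test another. At 1,080 per group, power for an 8-point difference in FCS change is about 49–83%, depending on the baseline (48% or 34%) and on r between 0 and 0.5.

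This rests on 20% loss, the plan's design effect of 1.5 applied in full, a comparison arm that does not change, binary FCS (no SD is given for continuous FCS), and one pairwise test at two-sided 0.05 without multiplicity adjustment. Power may be adequate under favourable values of r or of the design effect, but the documents do not show it. The between-group statement is unsupported as written and should be corrected.

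**What to change.** Delete the between-group sentence in section III.B, or restate it for the contrast to be tested.

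1. **Keep group-by-time.** Give the detectable difference in change at 1,080 per group with a stated r and design effect. For r = 0 to 0.3 this is about 10–12 points at the 48% baseline and 9–11 points at 34%.
2. **Or name a baseline-adjusted endline comparison for Basic vs Enhanced.** With the two-proportion variance multiplied by (1 − r²), power at r = 0.2–0.3 is about 80–82% for 48% vs 40% and 86–88% for 34% vs 26%. This relies on the random allocation described in section II. Section V.C.5.A instead says the sites are allocated purposively, so the two must be reconciled first. It does not cover the livelihoods arm, whose kebeles were chosen on criteria; that comparison still needs option 1.

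In either case, state the loss adjustment used. If loss is handled by dividing by 0.8, report about 78% power for the 48% to 40% row at 1,080 rather than enlarging the sample. Also reconcile the nine woredas with the eight in Table 2: state 960 per arm, or say which additional kebeles supply the other 120 (footnote 4 already allows additional kebeles within a woreda).

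The cost is protocol wording, with no households beyond the planned 1,080 per group. The price is a less favourable stated detectable difference under option 1, or a changed primary contrast under option 2, which should be fixed before endline data are seen.
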